7.2.2. Dose Escalation

7.2.2.1. Dose-Limiting Toxicity Determination

Dose-limiting toxicity is defined as an AE during Cycle 1 that is considered by the investigator to be at least possibly related to LY3164530 and fulfills any one of the following criterion using the National Cancer Institute (NCI) Common Terminology Criteria for Adverse Events (CTCAE) v 4.03:

- \geq Grade 3 non-hematological toxicity. Exceptions will be made for:

- nausea, vomiting, diarrhea, and constipation that can be controlled with treatment. Grade 3 and Grade 4 nausea, vomiting, or diarrhea should be considered DLTs if persisting more than 48 hours despite supportive intervention.
 - Grade 3 rash that resolves with treatment to \leq Grade 1 within 14 days
 - Grade 3 or 4 asymptomatic electrolyte abnormalities that respond to standard treatment
 - Grade 3 elevations of ALT and/or AST lasting fewer than 8 days, without evidence of other hepatic injury, in the setting of preexisting hepatic metastasis and baseline elevation of these values, may not be considered a DLT if agreed by the study investigator and Lilly CRP/CRS.
- Grade 4 neutropenia or leukopenia, of >7 days duration.
 - Grade 4 thrombocytopenia of any duration.
 - Grade 3 thrombocytopenia with bleeding.
 - Any febrile neutropenia.
 - Any other significant toxicity deemed by the primary investigator and Lilly clinical research personnel to be dose limiting (eg, any toxicity that is possibly related to the study drug that requires the withdrawal of the patient from the study during Cycle 1).

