6.13. Safety Analyses

All patients who receive at least 1 dose of LY3164530 will be evaluated for safety and toxicity. Adverse event (AE) terms and severity grades will be assigned by the investigator using National Cancer Institute Common Terminology Criteria for Adverse Events (NCI CTCAE) Version 4.03.

Safety analyses will include summaries of the following:

- Adverse events, including severity and possible relationship to study drugs
- Dose delays and dose adjustments
- Laboratory values
- Vital signs
- Dose-limiting toxicities at each dose level
- Electrocardiogram readings
- Deaths on treatment and within 28 +/- 5 days of treatment discontinuation

Hospitalizations and transfusions during the study treatment period or during the 28 +/- 5 days - day postdiscontinuation follow-up period will be summarized.

Dose Limiting Toxicity

Dose-limiting toxicity is defined as an AE during Cycle 1 that is considered by the investigator to be at least possibly related to LY3164530 and fulfills any one of the following criterion using the NCI CTCAE Version 4.03:

- \geq Grade 3 non-hematological toxicity. Exceptions will be made for:

- nausea, vomiting, diarrhea, and constipation that can be controlled with treatment. Grade 3 and Grade 4 nausea, vomiting, or diarrhea should be considered DLTs if persisting more than 48 hours despite supportive intervention.
 - Grade 3 rash that resolves with treatment to \leq Grade 2 within 8 days
 - Grade 3 or 4 asymptomatic electrolyte abnormalities that respond to standard treatment
 - Grade 3 elevations of ALT and/or AST lasting fewer than 8 days, without evidence of other hepatic injury, in the setting of preexisting hepatic metastasis. Baseline elevation of these values may not be considered a DLT if agreed by the study investigator and Lilly CRP/CRS.
- Grade 4 neutropenia or leukopenia, of >7 days duration.
 - Grade 4 thrombocytopenia of any duration.
 - Grade 3 thrombocytopenia with bleeding.
 - Any febrile neutropenia.
 - Any other significant toxicity deemed by the primary investigator and Lilly clinical research personnel to be dose limiting (eg, any toxicity that is possibly related to the study drug that requires the withdrawal of the patient from the study during Cycle 1).

DLT-Equivalent Toxicities

A DLT-equivalent toxicity is defined as an AE occurring in Cycle 2 and beyond that would have met the criteria for a DLT if it had occurred during Cycle 1.

Dose Escalation Method

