Dose escalation will be driven by an mTPI method (Ji and Wang 2013) ([Appendix 1](#)). A 3+3 design is commonly used in Phase 1 trials due to its simple, intuitive, and pre-specified escalation rules. However, the 3+3 method has been criticized for being conservative because the method is dictated by the observed DLT rate without acknowledging the variability arising from small cohort size.

Like the 3+3 design, the mTPI method incorporates pre-specified escalation rules. In contrast, the mTPI method is based on quantitative models that incorporate uncertainty into the decision rules, thereby allowing more aggressive dose escalation. In the mTPI method, the number of patients in each cohort is not fixed, but a minimum of 3 patients are required for this study at each dose (unless the rule in the table indicates to deescalate the dose due to unacceptable toxicity [DU]). If 3 to 6 patients are enrolled in a cohort, the escalation rule parallels a traditional 3+3 design. However, the stay/de-escalation rule of the mTPI is more aggressive than the 3+3 design. For instance, with 2 to 3 DLTs per 6 patients enrolled, the mTPI would recommend staying at the current dose, whereas the 3+3 design would recommend de-escalation. [Figure JNBA.6.1](#) provides the mTPI escalation rules for any cohort size up to 20 patients.

In [Figure JNBA.6.1](#), the number of patients dosed at a given dose level are shown in the columns (x-axis), while the number of DLTs experienced are shown in the rows (y-axis). The rules in this figure will be used for each dose level evaluated; the patient numbers and DLTs do not carry over from cohort to cohort. By locating the intersection of the number of patients dosed and the number of DLTs, 1 of 4 pre-defined rules is used:

- E: Escalate the dose
- S: Stay at the same dose
- D: Deescalate the dose
- DU: Deescalate the dose due to unacceptable toxicity. The dose cannot be re-escalated to this dose level at a future point in the escalation.

If agreed upon by the investigators and Sponsor (for instance, if PK/PD data suggest that increasing the dose further is not expected to yield additional benefit), a more conservative rule may be applied. For instance, if the rule indicates “E” to escalate, the dose may remain at the current dose level or be deescalated to a lower level.

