Figure JNBA.6.1. Dose-finding spreadsheet of the modified toxicity probability interval method.

The beginning dose level will be 300 mg. The dose will be escalated by a maximum increment of 100%. If the beginning dose level is determined to be unacceptably toxic, a -1 dose level may be explored.

The exact increment will be determined by the investigators and Lilly CRP/CRS, and may be less than the maximum increment allowed in the protocol. Safety data will be the primary criteria for both the decision to dose-escalate and for selecting the dose to be administered in the next cohort. In addition, if available at the time of the dose escalation decision, PK (maximum plasma concentration [C_{max}], area under the plasma concentration-time curve [AUC], and CL) and/or PD results will be used as secondary/supporting data for dose escalation. No dose escalation can occur without prior discussion and agreement between the investigator and the Lilly CRP or CRS; the decision will be documented in writing. Inpatient dose escalations are not permitted.

In Cohort 1 only, the first patient is required to complete a full cycle (28 days) before subsequent patients can be dosed. Subsequent patients in Cohort 1 can be dosed concurrently. Beginning with Cohort 2, patients within a cohort can be dosed concurrently.

The decision to stop dose escalation will be primarily driven by the appearance of DLTs and the rules in [Figure JNBA.6.1](#). However, if PK/PD data suggest that increasing the dose further is not expected to yield additional benefit, escalation may cease.

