6.13.1. Recommended Phase 2 Dose Determination

The RP2D will be a dose at which at least 10 patients, but no more than 20, have been enrolled. The RP2D will be agreed upon following discussion between the investigators and the Lilly CRP or CRS and will include an assessment of safety, PK, and PD data. At the RP2D, the intersection of the number of patients dosed and the number of DLTs at that dose level on the mTPI grid should indicate “S” or “E”.

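### SAP 6.13 breaks the protocol's liver-enzyme exemption in two, so some events that are DLTs under the protocol need not count under the SAP

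*SAP*

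**What the plan says.** Both documents treat a related non-haematological toxicity of Grade 3 or worse in Cycle 1 as a DLT, and both then list exceptions. One exception covers Grade 3 ALT/AST rises that last less than 8 days with no other sign of liver injury.

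- **Protocol 7.2.2.1** makes this a single conditional sentence: "in the setting of preexisting hepatic metastasis and baseline elevation of these values, may not be considered a DLT if agreed by the study investigator". The sponsor's clinical research physician or scientist must agree too.
- **SAP 6.13** (Dose Limiting Toxicity) reads: "in the setting of preexisting hepatic metastasis. Baseline elevation of these values may not be considered a DLT if agreed by the study investigator". It names the same sponsor representative.

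The SAP opens its definition with "Dose-limiting toxicity is defined as an AE during Cycle 1" and closes with a catch-all: "Any other significant toxicity deemed by the primary investigator and Lilly clinical research personnel to be dose limiting".

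The SAP uses the definition in two outputs. Its safety summaries include "Dose-limiting toxicities at each dose level". SAP 6.13.1 adds a grid check, which calls for S or E at this cell: "At the RP2D, the intersection of the number of patients dosed and the number of DLTs at that dose level on the mTPI grid".

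**The concern.** The full stop changes the rule. What stands before it is a complete entry in the list of exceptions, and its only patient condition is liver metastasis. Baseline elevation and agreement have moved to a separate sentence that says something else.

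Two groups of events are DLTs under the protocol but exempt under the SAP's literal text:

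1. Transient Grade 3 rises in patients with liver metastasis and normal baseline ALT/AST.
2. Such rises in patients with raised baseline values when agreement is not given.

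The default is also reversed. Under the protocol the investigator and sponsor must agree to exempt the event. Under the SAP they would have to agree to count it, through the catch-all.

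The DLT count is the quantity behind the primary objective. If the SAP is applied as written, the reported count at a dose can be one lower than the protocol's count for the same patients, in the less cautious direction.

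**Working it through.** **1. The conditions side by side**

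| Condition for exemption | Protocol 7.2.2.1 | SAP 6.13, first sentence |
|---|---|---|
| Grade 3, under 8 days, no other liver injury | required | required |
| Liver metastasis | required | required |
| Raised baseline ALT/AST | required | absent |
| Investigator and sponsor agree | required | absent |

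The SAP's second sentence does not supply the two missing rows. It says that a baseline elevation may be excused as a DLT, but a DLT is by definition a Cycle 1 adverse event at least possibly related to the drug. A pre-dose value never qualifies, so there is nothing to excuse.

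**2. Can the affected patients enrol?** Protocol 6.1.1 sets only upper limits for ALT and AST: 3 times ULN, or 5 times ULN with liver involvement. Patients with liver metastasis and normal baseline enzymes are eligible.

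**3. Could an amendment explain the difference?** The Amendment (b) summary lists no change to Protocol 7.2.2.1.

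**4. What one uncounted event does on the grid**

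Inputs from the documents: target rate 0.30 and equivalence interval (0.287, 0.301), from Protocol 7.2.2.3 and SAP 6.13. Assumptions, because the documents state neither: a Beta(1,1) prior, and DU when the decision is D and P(p > 0.30) > 0.95.

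With x DLTs in n patients the posterior is Beta(1 + x, 1 + n − x). The unit probability mass (UPM) is the posterior probability of an interval divided by its length. The lengths are 0.287 (E), 0.014 (S) and 0.699 (D). The largest UPM gives the decision.

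The plan's own figure comes first. This rule reproduces every printed cell for 0 to 5 DLTs at all n up to 20, and columns 3, 6 and 10 wherever they can be read. Those readable cells are the same in the protocol and SAP grids.

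| DLTs/n | UPM E | UPM S | UPM D | Cell |
|---|---|---|---|---|
| 0/3 | 2.58 | 1.41 | 0.34 | E |
| 1/3 | 1.13 | 1.76 | 0.93 | S |
| 1/6 | 2.24 | 2.17 | 0.47 | E |
| 2/6 | 1.13 | 2.25 | 0.92 | S |
| 4/10 | 0.64 | 2.14 | 1.13 | S |
| 5/10 | 0.22 | 1.07 | 1.32 | D |

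For example, at 5/10 the posterior probabilities of the three intervals are 0.0644, 0.0150 and 0.9206. Then 0.0644/0.287 = 0.22, 0.01496/0.014 = 1.07 and 0.9206/0.699 = 1.32. P(p > 0.30) = 0.922 is below 0.95, so the cell is D and not DU.

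Removing one DLT therefore moves 1/3 (S) to 0/3 (E), 2/6 (S) to 1/6 (E), and 5/10 (D) to 4/10 (S).

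**5. All counts at n = 10, the RP2D minimum**

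| Change in count | Change in cell |
|---|---|
| 1 to 0 | E to E |
| **2 to 1** | **S to E** |
| 3 to 2 | S to S |
| 4 to 3 | S to S |
| **5 to 4** | **D to S** |
| **6 to 5** | **DU to D** |
| 7 to 6, and each step up to 10 to 9 | DU to DU |

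The cell changes at 3 of 10 counts. It goes from failing to passing the S-or-E check at 1 of 10 (5 to 4). Rows 7 to 10 of this column are not legible in the available text and are taken from the recomputation.

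**The case against.** The strongest case for the plan has four parts.

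- **The words are all still there.** A comma and a conjunction became a full stop, so this looks like a slip, and the only reading that gives both halves of the bullet a purpose is the protocol's. That is a fair account of the cause. It also makes group 2 less clear-cut than group 1, because the agreement clause remains in the bullet. But a definition in an SAP should not depend on the reader repairing it from another document.
- **The protocol governs.** DLTs are judged as they occur, and both documents state "No dose escalation can occur without prior discussion and agreement between the investigator and the Lilly CRP or CRS". Protocol 7.2.3 contains the same RP2D grid check. In addition, "a more conservative rule may be applied", and the RP2D follows discussion of safety, PK and PD data. This stands. A changed cell forces no decision, and the exposure lies mainly in the SAP's own table and check. The escalation examples at 3 and 6 patients show how sensitive the grid is and are not predictions.
- **No re-adjudication is described.** If the table simply lists DLTs as judged during the study, it will match the protocol. True, but the SAP prints its own definition next to the table it governs and nowhere says that the protocol's judgement is used instead.
- **The effect may be rare.** At a true rate of 30%, exactly 5 DLTs in 10 has probability 252 × 0.3⁵ × 0.7⁵ = 0.10, before requiring that one of them is this liver event. This stands too, as a limit on size.

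The SAP is Version 1 and lags the protocol elsewhere. Its rash exemption, in the same list, also differs: Grade 2 or lower within 8 days, against Grade 1 or lower within 14 days in the protocol. That is a separate discrepancy and does not excuse this one.

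**Conclusion.** The concern holds. As written, the SAP's liver-enzyme exemption is more permissive than the protocol's. It omits two of the protocol's conditions from the operative sentence and leaves a sentence that cannot be applied. The wording conflict is certain and rests on no assumption.

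Its consequence is limited. One reclassified event matters only at a grid boundary, which at 10 patients means 3 of 10 counts for the cell and 1 of 10 for RP2D eligibility. These are counts of grid positions, not probabilities. They rest on the printed cells and, for 7 to 10 DLTs, on the assumed prior and DU cut-off. The frequency of the liver events cannot be obtained from the documents. The correction should be made because the count serves the primary objective and the error runs in the less cautious direction.

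**What to change.** In SAP 6.13, replace the full stop after the word metastasis with a conjunction and add a comma after the word values, so that the bullet reads as the protocol does: "in the setting of preexisting hepatic metastasis and baseline elevation of these values, may not be considered a DLT if agreed by the study investigator". The rest of the bullet already matches.

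The cost is one SAP sentence, with no protocol amendment, no extra tests and no extra patients. A few more events may count as DLTs than under the present SAP text, as the protocol already requires. The rash exemption in the same list should be aligned in the same edit.

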As shown in [Figure JNBA.1](#), if 1 of 3 patients experiences a DLT, the decision (located in column 3 row 1) is “S”, stay at the same dose. Therefore, the next patient must be treated at the same dose level. If 1 of 6 patients experience a DLT, the decision (located at column 6 row 1) is “E”, escalate the dose. However, if 2 of 3 patients experience a DLT the decision is “D” and the dose must be deescalated.

In the mTPI, the cohort size is not fixed. However, each cohort in this study will contain a minimum of 3 patients, unless the escalation rules dictate that the dose should be deescalated due to unacceptable toxicity (“DU”). Doses can be escalated, deescalated, and re-escalated following the rules in [Figure JNBA.1](#). If the dose decision was “DU,” the dose cannot be re-escalated to that level.

This study is designed to identify a dose level with a dose-limiting target toxicity rate of 30%. In reality, the exact target toxicity rate is almost never achieved for a dose. To this end, instead of using a single target rate, the mTPI method considers an equivalence interval (EI) around the target toxicity rate. For this study, the EI is calibrated to be (28.7%, 30.1%), resulting in the rules in [Figure JNBA.1](#). If the observed toxicity rate exceeds 40% and the model is still recommending “S”, the Sponsor, in discussion with the investigators, may choose to deescalate. Deescalation may not be required for toxicities confounded by patient comorbidities or other clinical factors that make direct attribution to study drug difficult to determine, particularly if

they are deemed non-serious (eg, fatigue, anorexia), reversible, or inconsistent with the known toxicities of MET or EGFR inhibitors by study investigators and the Lilly CRP/CRS.

		Number of patients treated at current dose																			
		1	2	3	4	5	6	7	8	9	10	11	12	13	14	15	16	17	18	19	20
Number of DLTs	0	E	E	E	E	E	E	E	E	E	E	E	E	E	E	E	E	E	E	E	E
	1	D	S	S	S	S	E	E	E	E	E	E	E	E	E	E	E	E	E	E	E
	2		DU	D	S	S	S	S	S	S	S	E	E	E	E	E	E	E	E	E	E
	3			DU	DU	D	S	S	S	S	S	S	S	S	S	S	E	E	E	E	E
	4				DU	DU	DU	D	D	S	S	S	S	S	S	S	S	S	S	S	S
	5					DU	DU	DU	DU	DU	D	S	S	S	S	S	S	S	S	S	S
	6						DU	DU	DU	DU	DU	DU	D	S	S	S	S	S	S	S	S
	7							DU	D	D	S	S	S	S	S						
	8								DU	D	S	S									
	9									DU	D										
	10										DU										
	11											DU									
	12												DU								
	13													DU							
	14														DU						
	15															DU	DU	DU	DU	DU	DU
	16																DU	DU	DU	DU	DU

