As shown in [Figure JNBA.6.1](#), if 1 of 3 patients experiences a DLT, the decision (located in column 3 row 1) is “S”, stay at the same dose. Therefore, the next patient must be treated at the same dose level. If 1 of 6 patients experience a DLT, the decision (located at column 6 row 1) is “E”, escalate the dose. However, if 2 of 3 patients experience a DLT the decision is “D” and the dose must be deescalated.

In the mTPI, the cohort size is not fixed. However, each cohort in this study will contain a minimum of 3 patients, unless the escalation rules dictate that the dose should be deescalated due to unacceptable toxicity (“DU”). Doses can be escalated, deescalated, and re-escalated following the rules in [Figure JNBA.6.1](#). If the dose decision was “DU,” the dose cannot be re-escalated to that level.

This study is designed to identify a dose level with a dose-limiting target toxicity rate of 30%. In reality, the exact target toxicity rate is almost never achieved for a dose. To this end, instead of using a single target rate, the mTPI method considers an equivalence interval (EI) around the target toxicity rate. For this study, the EI is calibrated to be (28.7%, 30.1%), resulting in the rules in [Figure JNBA.6.1](#). If the observed toxicity rate exceeds 40% and the model is still recommending “S”, the Sponsor, in discussion with the investigators, may choose to deescalate.

		Number of patients treated at current dose																			
		1	2	3	4	5	6	7	8	9	10	11	12	13	14	15	16	17	18	19	20
Number of DLTs	0	E	E	E	E	E	E	E	E	E	E	E	E	E	E	E	E	E	E	E	E
	1	D	S	S	S	S	E	E	E	E	E	E	E	E	E	E	E	E	E	E	E
	2		DU	D	S	S	S	S	S	S	S	E	E	E	E	E	E	E	E	E	E
	3			DU	DU	D	S	S	S	S	S	S	S	S	S	S	E	E	E	E	E
	4				DU	DU	DU	D	D	S	S	S	S	S	S	S	S	S	S	S	S
	5					DU	DU	DU	DU	DU	D	S	S	S	S	S	S	S	S	S	S
	6						DU	DU	DU	DU	DU	D	S	S	S	S	S	S	S	S	S
	7							DU	D	S	S	S	S	S	S						
	8								DU	D	S	S									
	9									DU	S										
	10										DU										
	11											DU									
	12												DU								
	13													DU							
	14														DU						
	15															DU	DU	DU	DU	DU	DU
	16																DU	DU	DU	DU	DU
	17																	DU	DU	DU	DU
	18																		DU	DU	DU
	19																			DU	DU
	20																				DU

E = Escalate to the next higher dose
 S = Stay at the current dose
 D = De-escalate to the next lower dose
 U = The current dose is unacceptably toxic
 Target DLT rate = 30%
 Equivalence interval = (28.7%, 30.1%)

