Appendix 1. Protocol JNBA mTPI and Simulation

The modified toxicity probability interval (mTPI) method employs a simple beta-binomial hierarchical model. Decision rules are based on calculating the unit probability mass (UPM) of 3 intervals corresponding to under dosing, proper dosing, and over dosing in terms of toxicity. Specifically, the under dosing interval is defined as $(0, p_T - \varepsilon_1)$, the overdosing interval as $(p_T + \varepsilon_2, 1)$, and the proper dosing interval as $(p_T - \varepsilon_1, p_T + \varepsilon_2)$, where ε_1 and ε_2 are small fractions, such as 0.05, to account for the uncertainty around the true target toxicity. A sensitivity analysis reported by Ji et al. (2010) showed that the mTPI design is robust to the specification of ε values.

In addition, ε_1 and ε_2 could take different values to reflect physician preference and the nature of the disease. For advanced diseases with few treatment options, higher toxicity rates might be considered acceptable, implying a specification of $\varepsilon_2 > \varepsilon_1$. For less advanced diseases, the 2 ε values could be identical or ε_1 could be $> \varepsilon_2$. The 3 dosing intervals are associated with 3 different dose-escalation decisions. The under-dosing interval corresponds to a dose escalation (E), overdosing corresponds to a dose de-escalation (D), and proper dosing corresponds to staying at the current dose (S).

Given an interval and a probability distribution, the UPM of that interval is defined as the probability of the interval divided by the length of the interval. The mTPI design calculates the UPMs for the three dosing intervals, and the one with the largest UPM implies the corresponding dose-finding decision. That decision provides the dose level to be used for future patients. For example, if the under dosing interval has the largest UPM, decision E, to escalate, will be executed, and the next cohort of patients will be treated at the next-higher dose level. Ji et al. (2010) show that the decision based on the UPM is optimal in that it minimizes a subsequent expected loss. Under the mTPI design, a trial is terminated when either the lowest dose is above the maximum tolerated dose (MTD) or a pre-specified maximum sample size is reached.

Simulation

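### The protocol and SAP state the same mTPI target and equivalence interval, but their printed grids differ at 6/11 and 6/12 DLTs, and the SAP's two cells could not be reproduced

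*SAP*

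**What the plan says.** Both documents fix the same design inputs. The SAP's target statement in 6.13, repeated in protocol 7.2.2.3, is "This study is designed to identify a dose level with a dose-limiting target toxicity rate of 30" per cent. On the interval, both write "For this study, the EI is calibrated to be (28.7%, 30.1%), resulting in the rules in" their own figure: Figure JNBA.1 in the protocol, Figure JNBA.6.1 in the SAP.

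SAP Appendix 1 and protocol Attachment 7 describe the model alike. The design "method employs a simple beta-binomial hierarchical model", and of the three dosing intervals "the one with the largest UPM implies the corresponding dose-finding decision". Neither document gives the beta prior or the posterior probability at which D becomes DU. The consequence of DU is stated: "DU: Deescalate the dose due to unacceptable toxicity. The dose cannot be re-escalated to this dose level at a future point in the escalation".

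Row 6 of the grid, read from n = 6 to n = 20, is:

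- Protocol Figure JNBA.1: "DU DU DU DU DU DU D S S S S S S S S"
- SAP Figure JNBA.6.1: "DU DU DU DU DU D S S S S S S S S S"

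The grid also enters the choice of RP2D. SAP 6.13.1 and protocol 7.2.3 ask for 10 to 20 patients at the dose and say that "the intersection of the number of patients dosed and the number of DLTs at that dose level on the mTPI grid should indicate" either stay (S) or escalate (E).

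**The concern.** One target and one interval, put through one model, give one grid. Two grids that claim the same calibration cannot both follow from it. The cells that differ fall inside the 10 to 20 patient range in which the RP2D is chosen:

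| DLTs / patients | Protocol | SAP | Consequence |
|---|---|---|---|
| 6/11 | DU | D | Return to the dose is barred in one document and open in the other |
| 6/12 | D | S | The grid part of the RP2D condition fails in one document and is met in the other |

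Each document points to its own figure for ongoing decisions (protocol 10.10, SAP 6.15), and neither says which grid prevails. The grid serves the primary objective, so a reader of the study report could not tell which rule a dose at 6/12 was judged by.

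**Working it through.** **Inputs.** From the documents: target 0.30, interval (0.287, 0.301), beta-binomial model, largest unit probability mass (UPM) decides. Assumed: Beta(1,1) prior, and DU when P(p > 0.30 | data) > 0.95.

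**Formulas.** With x DLTs in n patients the posterior is Beta(1 + x, 1 + n − x), with distribution function F.

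- UPM(E) = F(0.287) / 0.287
- UPM(S) = [F(0.301) − F(0.287)] / 0.014
- UPM(D) = [1 − F(0.301)] / 0.699

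**Reproducing the printed grids.** Rows 0 to 6 are complete in both documents and hold 20 + 20 + 19 + 18 + 17 + 16 + 15 = 125 cells. The two documents agree throughout rows 0 to 5. The calculation reproduces 125 of 125 protocol cells and 123 of 125 SAP cells. The two misses are 6/11 and 6/12.

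**The disputed cells.**

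- 6/12, posterior Beta(7,7): UPM(E) = 0.04996 / 0.287 = 0.174; UPM(S) = 0.013455 / 0.014 = 0.961; UPM(D) = 0.93659 / 0.699 = 1.340. The largest is D. P(p > 0.30) = 0.938, so not DU.
- 6/13, posterior Beta(7,8): UPM(S) = 1.357 against UPM(D) = 1.295. S therefore begins at n = 13.
- 6/11, posterior Beta(7,6): P(p > 0.30) = 0.961, so DU at 0.95.

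**Does the choice of cut-off matter?** Under Beta(1,1) the SAP's DU at 5/9 needs a cut-off below 0.9527, while its D at 6/11 needs one of at least 0.9614. No single cut-off does both. The protocol rows fit any cut-off from about 0.942 to 0.953. The cut-off cannot turn 6/12 into S, because S against D depends only on the UPMs.

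**Does the choice of prior or interval matter?**

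- At the stated interval, 33,300 combinations of prior (both parameters 0.1 to 3.0) and cut-off (0.90 to 0.99): 28 reproduce protocol rows 0 to 6, none reproduces the SAP's.
- With Beta(1,1), 14,800 combinations of interval (lower limit 0.20 to 0.295, upper 0.301 to 0.396) and cut-off: 205 reproduce the protocol's rows, none the SAP's.
- The best SAP fit in either scan has 2 misses. Some settings match part or all of SAP row 6 alone, such as Beta(0.6, 1.4) for S at 6/12, or an interval of about (0.27, 0.39) with cut-off 0.97 for the row. They break other cells, and the latter also departs from the stated interval.

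**Internal check on the SAP.** At an observed 50% rate the SAP prints 4/8 = D, 5/10 = D, 6/12 = S, while P(p > 0.30) under Beta(1,1) rises: 0.901, 0.922, 0.938.

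**How often would 6/12 arise?** Assume patients are added only while the cell reads S, and a dose once left is not revisited. The cells passed on the way are the same in both grids. For cohorts of 6, only 2/6 and 3/6 read S, so the probability is P(2)P(4) + P(3)²:

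- true rate 50%: 0.2344 × 0.2344 + 0.3125² = 0.153
- true rate 40%: 0.3110 × 0.1382 + 0.2765² = 0.119

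The other patterns were calculated in the same way:

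| Enrolment pattern | True rate 40% | True rate 50% |
|---|---|---|
| One by one after the first 3 | 1.1% | 1.4% |
| Cohorts of 3 | 3.8% | 4.8% |
| Cohorts of 6 | 11.9% | 15.3% |
| Fixed n = 12, grid ignored | 17.7% | 22.6% |

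One by one, 6/11 cannot be reached, because both 5/10 (D) and 6/10 (DU) already stop enrolment in both grids.

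**The case against.** **The table may have been misread.** Rows 7 to 14 have lost cells in both documents, and the protocol's own figure comes out differently in rows 8 and 9 between 7.2.2.3 and its reprint in Attachment 8. The SAP's row 6 is the protocol's with one DU fewer and one S more, which a dropped cell with filling at the end would also produce. This stands in part. Row 6 has 15 cells in both documents, so a simple lost cell is not enough, and the reprint in Attachment 8 repeats the protocol's row 6. A compensating misread still cannot be excluded. A reader might cite rows 7 and 9 as further evidence; in their damaged state they support nothing.

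**The prior and cut-off are not stated.** This stands as a limit. A reader might infer that SAP row 6 is impossible under any mTPI model. The documents do not support that; the result is conditional on Beta(1,1), extended by the scans.

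**There are safeguards.** SAP 6.13 lets the sponsor, with the investigators, de-escalate when the observed rate exceeds 40% and the grid reads S, and 6/12 is 50%. A more conservative rule may be agreed at any time, and the RP2D also needs agreement and a review of safety, PK and PD data. So it does not follow that a dose at 6/12 would become the RP2D under the SAP. These provisions are discretionary, however, and do not make the grids agree.

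**The SAP is the older document.** It describes only dosing on Days 1 and 15, while the protocol has been amended to add a weekly schedule. That may explain a stale figure, but target and interval are unchanged, so no intended change of rule is visible.

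**Conclusion.** The point holds as a contradiction between two printed decision grids that claim the same calibration. It is confined, on the readable rows, to 6/11 and 6/12. It is worth correcting because both cells lie in the RP2D range, but the practical exposure is modest: at true DLT rates of 40% to 50%, arrival at 6/12 has a probability of about 1% to 15%, depending on how patients are grouped. The figures of 18% to 23% that a fixed sample of 12 would suggest overstate it, because they ignore stopping along the way.

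The conclusion rests on the transcription of row 6 being faithful. The statement that the SAP's two cells do not follow from the model rests further on Beta(1,1) and a 0.95 cut-off, supported by the scans. That the protocol's rows reproduce is a finding about arithmetic. It might be taken to settle which de-escalation rule should apply to patients, but the documents do not support that step, and the passages need to be reconciled.

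**What to change.** 1. Check row 6 of SAP Figure JNBA.6.1 against the source figure. If it matches the protocol there, the discrepancy at these two cells falls away.
2. If the difference is in the source, reconcile the two passages: regenerate both figures from one documented calculation and carry the same single grid in both documents.
3. In either case, state the beta prior and the DU cut-off beside the target and interval, so that every cell can be reproduced.

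The cost is one short calculation, at most one replaced figure in each document, and a sentence on the prior and cut-off. No new data or change in sample size is needed.
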